### **15. STATISTICAL CONSIDERATIONS**

This section presents general information about statistical considerations and concepts such as randomization, stratification, statistical power, and sample size. There will also be a brief discussion on analysis methodology, as well as some data conventions. The detailed descriptions of statistical analysis methods and data conventions will be in a separate document, the Statistical Analysis Plan (SAP). Any post-hoc analyses will be identified in the final Clinical Study Report.

#### **15.1 Treatment Arms**

The following treatment arms will be assessed:

- active: Gelesis100 2.25 g, twice daily
- placebo: matching placebo containing sucrose, twice daily

## **15.2 Baseline and Visit Windows**

Baseline for a given parameter or endpoint is defined to be the last observation (obtained at either the Screening or Baseline Visit) taken before the first study product administration. The study visits and visit windows are Days  $8 \pm 2$ ,  $15 \pm 2$ ,  $29 \pm 2$ ,  $43 \pm 2$ ,  $57 \pm 2$ ,  $71 \pm 2$ ,  $85 \pm 2$ ,  $113 \pm 3$ ,  $141 \pm 3$ ,  $169 \pm 3$ , 171, and  $197 \pm 3$ .

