### **11.1.3 Tertiary Endpoints**

- Body weight responders ( $\geq 10\%$  weight loss from baseline to Day 171)
- Estimated excess body weight (percent change from baseline to Day 171)
- Body weight status (normal, overweight, obese) (change from baseline to Day 171)
- Waist circumference (change from baseline to Day 171)
- Serum insulin (percent change from baseline to Day 171)
- Serum C-reactive protein (CRP) (change from baseline to Day 171)
- Serum total cholesterol (percent change from baseline to Day 171)
- Serum LDL cholesterol (percent change from baseline to Day 171)
- Serum high-density lipoprotein (HDL) cholesterol (percent change from baseline to Day 171)
- Serum total cholesterol/HDL cholesterol ratio (change from baseline to Day 171)
- Serum triglycerides (percent change from baseline to Day 171)
- Supine and standing SBP and DBP (change from baseline to Day 171)
- Food intake (change from baseline to Day 169)
- Food habits (change from baseline to Day 169)
- Satisfaction (overall impression on Day 169)
- Impact of weight on quality of life (IWQOL) (change from baseline to Day 171) (at selected sites)

The secondary and tertiary effectiveness endpoints are for supportive purposes only.

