### **11.2.4 Laboratory Tests**

- Hematology including hemoglobin, hematocrit, red blood cell count, reticulocyte count, white blood cell count with differential, and platelet count
- Blood chemistry including plasma glucose and serum sodium, potassium, chloride, calcium, phosphorous, magnesium, blood urea nitrogen, creatinine, uric acid, total cholesterol, LDL cholesterol, HDL cholesterol, triglycerides, total protein, albumin, total bilirubin, alkaline phosphatase, lactate dehydrogenase, alanine aminotransferase, aspartate aminotransferase, and gamma glutamyltransferase
- Vitamins including vitamin A, vitamins B1, B2, B6, B9, and B12, vitamin D, and vitamin E (vitamins will be measured in approximately 60 subjects from the sites of Czech Republic and the site of Rome, Italy)

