### **12.2.1 Visit 1 (Screening Visit; Day -21 to -1)**

- Informed consent (women of childbearing potential are requested to use a medically approved contraceptive method during the entire study)
- Demographic characteristics (gender, age, ethnic origin)
- Menopausal status (and estrogen replacement therapy status)
- Smoking status
- Medical history
- Physical examination
- Height
- Weight
- Waist circumference
- Vital signs (supine and standing blood pressure and heart rate)
- ECG
- Binge eating disorder (QEWP-R)
- Dietary interview (calculation of the energy requirement)
- Serum pregnancy test (women of childbearing potential only)
- TSH
- Urine drug screen (test performed at the Investigator's site)
- HbA1c
- Hematology
- Blood chemistry
- Previous (within 1 month) and concomitant medication records
- AEs and SAEs records

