### **15.5.2 Stratification**

The following characteristics at the Screening Visit will be used as stratification factors at the time of randomization and the centralized randomization procedure will balance treatment arm assignments in each country or combination of countries for the following stratification factors:

- male, BMI < 35, and normal fasting glucose
- male, BMI < 35, and impaired/diabetic fasting glucose
- male, BMI  $\geq$  35, and normal fasting glucose
- male, BMI  $\geq$  35, and impaired/diabetic fasting glucose
- female, BMI < 35, and normal fasting glucose
- female, BMI < 35, and impaired/diabetic fasting glucose
- female, BMI  $\geq$  35, and normal fasting glucose
- female, BMI  $\geq$  35, and impaired/diabetic fasting glucose

The selection of these stratification factors is based on the facts that gastric capacity has a tendency to be higher in male subjects and in subjects with higher BMI, and weight loss can be more important in subjects with higher fasting glucose (data from the FLOW study).

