### **15.7.2 Covariates**

For effectiveness analyses, the stratification factors and the respective baseline values for the endpoint will be used as covariates in the analysis models.

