### **Secondary and tertiary endpoints**

Analysis of the secondary and tertiary endpoints will be summarized according to the variable type:

- continuous data summaries will be based on ANCOVA or Mixed Model using the stratification factors and the respective baseline values for the endpoint as a covariate in the model
- categorical data summaries will be based on Logit model using the stratification factors and the respective baseline values for the endpoint as a covariate in the model

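### Adding the Screening value as a second ANCOVA covariate would slightly sharpen the continuous metabolic, blood-pressure and waist endpoints at almost no cost; this is an improvement, not an error

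*Combined protocol and SAP*

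**What the plan says.** Section 15.2 takes one value per parameter as baseline: "the last observation (obtained at either the Screening or Baseline Visit) taken before the first study product administration". Where both visits measure a variable, that is the Visit 2 value. Section 15.7.2 then says that "the stratification factors and the respective baseline values for the endpoint will be used as covariates in the analysis models". Sections 15.8 and 15.8.6.1 repeat this for ANCOVA and Logit.

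Sections 12.2.1 and 12.2.2 list HbA1c, blood chemistry, waist and vital signs at both visits. The vital signs entry at Visit 1 reads "Vital signs (supine and standing blood pressure and heart rate", and Visit 2 has the same item. Section 11.2.4 defines the chemistry panel as "Blood chemistry including plasma glucose and serum sodium, potassium" and further analytes, which include the lipids. Serum insulin is listed at Visit 2 but not at Visit 1. The screening period lasts at most 21 days (Section 10.1.1).

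Some Screening information does reach the models. Section 15.5.2 states: "The following characteristics at the Screening Visit will be used as stratification factors at the time of randomization". These are gender, BMI class and fasting glucose status (normal versus impaired/diabetic).

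On the standing of the endpoints, Section 11.1.3 says: "The secondary and tertiary effectiveness endpoints are for supportive purposes only".

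**The concern.** Glucose, lipids and blood pressure vary within a person from day to day, so the value at one visit is a noisy measure of where the subject started. A second reading of the same variable, also taken before randomization, usually carries some further information. ANCOVA on both readings then leaves less residual variance than ANCOVA on one. The second reading is already collected, and no model described in the protocol uses it in continuous form.

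At stake is the width of the intervals for plasma glucose and HbA1c, which are secondary endpoints and named objectives in Section 6.2, and for the tertiary lipid, blood-pressure and waist endpoints. The secondary endpoints are to be tested in a fixed order (Section 15.7.4), so lost precision on one can also block those below it.

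**Working it through.** **1. The plan's own figure.** Section 15.4 gives 161 completers per arm, SD 5.0%, delta 4.5%, margin 3.0% and one-sided alpha 0.05. The excess over the margin is 4.5 − 3.0 = 1.5. The standard error is 5 × √(2/161) = 0.557. Power = Φ(1.5/0.557 − 1.645) = Φ(1.047) = 0.852, which matches the stated 85%. This figure is for body weight and is not affected. The documents state no power for the endpoints considered here.

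**2. Formula.** Let rb and rs be the correlations of the Visit 2 and Visit 1 values with the Day 171 value, and ρ the correlation between Visits 1 and 2. The residual variance, as a fraction of the outcome variance, is:

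- plan's model: 1 − rb²
- with Visit 1 added: 1 − (rb² + rs² − 2·rb·rs·ρ)/(1 − ρ²)

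The SE ratio is the square root of the second over the first. The documents give no correlations, so all are assumptions.

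| rb, rs, ρ | Residual variance | Change in SE |
|---|---|---|
| 0.5, 0.5, 0.5 | 0.750 → 0.667 | −5.7% |
| 0.7, 0.7, 0.7 | 0.510 → 0.424 | −8.9% |
| 0.9, 0.9, 0.9 | 0.190 → 0.147 | −11.9% |
| 0.7, 0.65, 0.8 | 0.510 → 0.487 | −2.2% |
| 0.7, 0.56, 0.8 | 0.510 → 0.510 | 0% |

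The first three rows are favourable cases: they treat Day 171 as no further from baseline than Screening is. In the last row rs = rb × ρ, so Screening adds nothing. Simulated SE ratios there were 1.0015 (322 subjects) and 1.0012 (460), a loss of 0.1-0.2%.

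**3. A more realistic structure.** Let R = between-person variance/(between + within-person variance), and let r be the correlation of the subject's true level between baseline and follow-up. Then ρ = R and rb = rs = r·R, and the SE ratio becomes √{[1 − 2(rR)²/(1 + R)] / [1 − (rR)²]}.

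| Variable (assumed between/within SD) | R | r = 0.5 | r = 0.75 | r = 0.9 |
|---|---|---|---|---|
| Glucose 12/5 mg/dL | 0.852 | −0.9% | −2.8% | −5.9% |
| Glucose 12/7 mg/dL | 0.746 | −1.2% | −3.4% | −6.2% |
| HbA1c 0.4/0.05 points | 0.985 | −0.1% | −0.5% | −1.4% |
| HbA1c 0.4/0.2 points | 0.800 | −1.1% | −3.2% | −6.2% |

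Example, glucose 12/5 at r = 0.75: rR = 0.639; 1 − 0.408 = 0.592; 1 − 2 × 0.408/1.852 = 0.559; √(0.559/0.592) = 0.972.

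**4. Entry limits and the glucose stratum.** The formula ignores both, and both reduce the gain. With all correlations at 0.7 and 322 subjects, putting a two-level Screening status in both models cut the simulated gain from 8.8% to 4.8%. Simulations with entry truncation on Visit 1, the glucose stratum kept, 322 and 460 subjects and r = 0.75-0.9 gave SE reductions of 1.3-3.1% for glucose (up to 3.6% in one variant), 1.3-4.3% for LDL, 3-6% for supine systolic pressure and 0.3-6% for HbA1c. At r = 0.5 the reduction was 1% or less. Waist was not simulated.

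**5. In practical terms.** A fall in SE of 1%, 3% or 6% is worth 1/0.99² = 1.02, 1/0.97² = 1.06 or 1/0.94² = 1.13 times the subjects. For percent change in glucose at r = 0.75 and 322 completers, the 95% half-width moves from about 2.09 to 2.05 points.

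**6. Logit endpoints.** In simulated Logit models with 460 subjects, adding the covariate raised the SE of the log-odds ratio by 2-6%. The estimate moved further from zero and power rose by about 1 to 2 points. The interval does not narrow, and the quantity estimated changes.

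**The case against.** The strongest reply is that nothing here is wrong. The last pre-dose value with ANCOVA on strata and baseline is a standard, unbiased analysis. No stated figure changes, the endpoints are declared supportive, and the gain may be very small. All of that stands.

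Further points also hold:

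- The size rests on SDs and correlations that the documents do not give. For HbA1c, which may vary little within a person, the gain could be close to nil.
- Only two of the four metabolic objectives in Section 6.2 can benefit, because insulin and HOMA-IR have no Screening value.
- Supine pressure is already read twice per visit (Section 11.3.1.4) and waist three times (Section 11.3.1.3). Replicates within a visit do not remove day-to-day variation, however.
- Multiple imputation is planned (Section 15.7.3), and the relative gain after imputation was not assessed.
- Final detail is deferred: "The detailed descriptions of statistical analysis methods and data conventions will be in a separate document". The text reviewed does not include that document. If it already lists these covariates, nothing is needed.

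A reader might infer more than the documents support. Screening data are not wholly ignored: glucose status and BMI class enter every effectiveness model as strata. Narrower intervals are not assured, because they require Screening to add information beyond Visit 2. Nor would they extend to every endpoint: for plasma glucose status, "categorical data summaries will be based on Logit model using the stratification factors", and there the interval widens.

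**Conclusion.** The point holds as a modest, near-free gain in efficiency for supportive continuous endpoints. The plan contains no error here, and the co-primary analyses, sample size and 85% power are untouched. With true baseline-to-follow-up correlation of 0.75-0.9, the expected fall in SE is about 1-3% for glucose, 1-4% for LDL, 3-6% for supine systolic pressure and 0.3-6% for HbA1c. With correlation 0.5 it is 1% or less. These figures depend on assumed variances and should be read as a range.

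The balance still favours the change, since the worst case is a loss of 0.1-0.2% of the SE. Both readings precede randomization, so entering both as covariates does not bias the treatment comparison, even though subjects were selected on the Screening value.

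**What to change.** Add to the SAP before unblinding, with a matching line in Sections 15.2 and 15.7.2:

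- Keep the Visit 2 value for computing change and percent change.
- For plasma glucose, HbA1c, lipids, blood pressure and waist, include the Visit 1 value of the same variable as a second continuous covariate in the ANCOVA, beside the Visit 2 value and the strata. Do not average the two visits, because eligibility limits truncate the Screening value.
- If a subject was re-screened (Section 8.1 allows this for fasting glucose and lipids), use the last qualifying Screening value.
- For blood pressure, use the mean of the Screening readings in the arm selected for the study, since Section 11.3.1.4 has supine pressure measured in both arms at that visit.
- Leave the Logit model for plasma glucose status, and the models for insulin and HOMA-IR, unchanged.
- Carry the same covariates in the multiple-imputation model.

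The cost is a short paragraph and one degree of freedom per model, with no new visit, sample or endpoint definition. Added after unblinding, it would be post hoc.

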## **15.3 Description of Study Endpoints**

The details of the study endpoints are presented in Section 11.

## **15.4 Sample Size Determination and Rationale**

For this clinical trial, a total of 460 subjects (230 per arm) will be randomized to have 322 subjects complete the study (161 per arm) due to an anticipated dropout rate of 30%. This sample size will allow establishing both super-superiority and superiority with sufficient statistical power based on the primary endpoint of change in body weight from baseline.

The sample size calculation, using PASS (16), is based on the assumption that there will be a clinically meaningful difference of at least 3.0% weight loss between the two arms after 24 weeks of treatment. This 3.0% is also being used as margin to establish the super-superiority (lower bound of the confidence interval of Gelesis100 effect  $\geq 3.0\%$  of placebo effect). With the above sample size, there is 85% statistical power for a 3.0% margin super-superiority (i.e., delta of at least 4.5%) with a common SD of 5.0% and a type I error rate of 0.05 (one-sided test). The statistical formula for the study hypothesis is as follows:

$$H_0: \mu_{\text{placebo}} - \mu_{\text{Gelesis100}} < 3.0\%$$

$$H_A: \mu_{\text{placebo}} - \mu_{\text{Gelesis100}} \geq 3.0\%$$

Where  $\mu_{\text{placebo}}$  is the mean percent change from baseline in the placebo arm and  $\mu_{\text{Gelesis100}}$  is the mean percent change from baseline in the Gelesis100 arm.

In addition, with the above sample size, there will be at least 90% statistical power to establish that the difference between the two arms is greater than 0 (i.e., the superiority with no margin), with a common SD of 5.0% and a type I error rate of 0.05 (two-sided tests), with the null hypothesis that the mean percent change from baseline in primary effectiveness endpoint is the same for both treatment arms and the alternative hypothesis that the Gelesis100 arm provides a different mean percent change in body weight than does the placebo arm. The statistical formula for the study hypothesis is as follows:

$$H_0: \mu_{\text{placebo}} - \mu_{\text{Gelesis100}} = 0$$

$$H_A: \mu_{\text{placebo}} - \mu_{\text{Gelesis100}} \neq 0$$

Where  $\mu_{\text{placebo}}$  is the mean percent change from baseline in the placebo arm and  $\mu_{\text{Gelesis100}}$  is the mean percent change from baseline in the Gelesis100 arm.

---

## **15.5 Randomization, Stratification, Blinding, and Unblinding**

### **15.5.1 Randomization**

This is a multicenter randomized clinical trial with sites from different countries (US, Canada, and several European countries). Eligible subjects will be randomly assigned to the active arm or the placebo arm based on a randomization schedule. An individual independent of the clinical trial team will develop the randomization schedule.

The randomization will be central and will use mixed blocks of 2 and 4 with a 1:1 ratio of active to placebo to ensure even distribution of active and placebo subjects. Each arm will include approximately 230 subjects.

The randomization assignment will be made through an interactive web randomization system maintained by the CRO. The site representative will log into the eClinical system (developed by Clinical Research Technology, Srl.) and enter the information pertaining to the subject to be randomized, and will be notified of the next sequential randomized treatment.

### **15.5.2 Stratification**

The following characteristics at the Screening Visit will be used as stratification factors at the time of randomization and the centralized randomization procedure will balance treatment arm assignments in each country or combination of countries for the following stratification factors:

- male, BMI < 35, and normal fasting glucose
- male, BMI < 35, and impaired/diabetic fasting glucose
- male, BMI  $\geq$  35, and normal fasting glucose
- male, BMI  $\geq$  35, and impaired/diabetic fasting glucose
- female, BMI < 35, and normal fasting glucose
- female, BMI < 35, and impaired/diabetic fasting glucose
- female, BMI  $\geq$  35, and normal fasting glucose
- female, BMI  $\geq$  35, and impaired/diabetic fasting glucose

The selection of these stratification factors is based on the facts that gastric capacity has a tendency to be higher in male subjects and in subjects with higher BMI, and weight loss can be more important in subjects with higher fasting glucose (data from the FLOW study).

### **15.5.3 Blinding**

As this is a double-blind trial, the study participants, the Investigators, all other study site personnel, the Monitoring Team involved in collecting the data, the Data Management Team involved in querying the clinical sites, and the Sponsor will be blinded to treatment assigned to the subject during the entire course of the study. Placebo capsules matching

---

the size, shape, color, and coating of Gelesis100 will be used for blinding the study treatment.

The randomization lists containing the assignment of subjects to treatment arms will be securely provided to the person involved in randomizing the subjects (i.e., the WebMaster), who has no role in screening, qualifying, enrolling, or evaluating study subjects. No other study personnel other than the WebMaster and the randomization code generator will have access to the randomization codes for the study.

#### **15.5.4 Unblinding**

To maintain the study blind, treatment unblinding will occur only per the cases specified below. The unblinding will be performed after all clinical data have been received, data inconsistencies have been resolved, and the database has been locked, except for the case of the interim analysis by an independent statistician and the emergency unblinding including management of a suspected USADE/SADE.

##### ***15.5.4.1 Unblinding for Interim Analysis***

An interim analysis is planned to be conducted when approximately 50% of the subjects have been randomized and completed Visit 13 (Week 24) or early terminated, whichever comes first. The details of this interim analysis are presented in Section 15.6.

Unblinded treatment assignments for the interim analysis will only be given to the independent statistician. For this analysis, there will be no subject level unblinding to any other personnel in the study except the WebMaster and the randomization code generator. The summary tables will be unblinded to the treatment arm level and will be presented using masked treatment arms. Unblinding of treatment arms to the Data Monitoring Committee members will only occur per their request.

##### ***15.5.4.2 Unblinding for Emergency***

Every attempt will be made to maintain the blind throughout the study. Breaking the blind prematurely will be allowed only under two circumstances:

- when knowledge of the treatment assignment is essential for treating a subject in case of an emergency
- as part of the management of a suspected USADE/SADE

The unblinding of treatment assignment will be performed by:

**The Investigator** in case of a suspected SADE if:

- The information about the treatment assignment is essential for the subsequent treatment of the suspected SADE.

Should the need for unblinding the code arise, the Sponsor's Trial Monitor must be contacted immediately via phone and e-mail to approve the unblinding. This prior approval can be waived if there is a life-threatening situation requiring immediate

---

intervention. However, the Investigator must notify the Sponsor (or designee) as soon as possible following the unblinding event.

**The CRO Clinical Safety** in case of a suspected USADE/SADE if:

- The Regulatory Authorities/Ethics Committee/Institutional Review Board request the information about the treatment assignment.
- The Sponsor needs the information about the treatment assignment for the evaluation of risk analysis.

The CRO Clinical Safety performs such unblinding upon approval from the Sponsor. After unblinding, the CRO Clinical Safety Manager informs both the Sponsor and the Investigator about the study subject in question.

The unblinding is performed by logging onto the eClinical system and entering the appropriate subject-specific information. The user will follow the prompts for emergency unblinding and will be notified of the treatment assignment on the screen. The date and reason for revealing the treatment assignment for the subjects will be captured in the eClinical system. Sponsor and CRO Clinical Safety will be notified of the unblinding. Sponsor's Trial Monitor will follow up with the site in a case the site did not obtain prior approval to unblind.

Subjects who are unblinded for emergency reasons will be discontinued from the treatment.

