## **14. TREATMENT/STUDY DISCONTINUATION**

### **14.1 Temporary Treatment Discontinuation**

The subjects may discontinue the study treatment for a period not exceeding 3 days for a valid medical reason, at the discretion of the Investigator.

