### **14.2 Permanent Treatment/Study Discontinuation**

#### **14.2.1 Reasons**

The subject may withdraw from the treatment with the investigational product (and the study) at any time and irrespective of the reason.

The Investigator will discontinue the investigational product (and the study) for the following reasons (after assessing their clinical relevance):

- contraception cessation
- pregnancy or wish of pregnancy
- significant intolerance to the study product
- an increase of  $\geq 0.5\%$  point ( $\geq 5.5$  mmol/mol) in HbA1c from Baseline Visit in subjects with treated or untreated type 2 diabetes, or any increase if the new value falls in the

Property of Gelesis, Srl. – Strictly Confidential

---

range of the exclusion criteria for HbA1c (see Section 8.4) after confirmation following a re-check at the next study visit (or before)

- an increase of  $\geq 10\%$  in total cholesterol, LDL cholesterol, or triglycerides from Baseline Visit in subjects with elevated lipids at Baseline Visit, or any increase if the new values fall in the range of the exclusion criteria for lipids (see Section 8.4) after confirmation following a re-check at the next study visit (or before)
- an increase of  $\geq 10$  mm Hg in supine SBP and/or supine DBP from Baseline Visit in subjects with treated or untreated hypertension, or any increase if the new values fall in the range of the exclusion criteria for blood pressure (see Section 8.4) after confirmation following a re-check at the next study visit (or before), based on the mean of two consecutive readings
- poor subject compliance with the study procedures and recommendations and/or major protocol deviation
- it is the best interest of the subject (including the need to add prohibited medications)

The subject is withdrawn from the treatment and the study if the treatment arm is unblinded for emergency reasons (see Section 15.5.4.2) or for a reason other than the interim analysis before the end of the treatment.

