#### **14.2.2 Procedures**

When confirmed, a permanent treatment/study discontinuation should be recorded by the Investigator in the appropriate electronic CRF and, if applicable, reported to the relevant Ethics Committee/Institutional Review Board.

Every effort should be made to complete the clinical and laboratory evaluations required for Visits 12 and 13 as soon as possible (combined assessments).

Subjects who have withdrawn from the treatment/study cannot be re-enrolled in the study. Their screening number and randomization number must not be re-used.

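### A code break by CRO Clinical Safety needs no treatment reason, yet it withdraws the subject from the study whether or not the site learned the arm, at the cost of a Day 171 weight (low severity)

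*Combined protocol and SAP*

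**What the plan says.** Section 15.5.4.2 sets out two routes for breaking the code in a suspected serious adverse device effect (SADE, or USADE if unanticipated).

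- **Investigator route.** This requires a treatment need: "The information about the treatment assignment is essential for the subsequent treatment of the suspected SADE".
- **CRO Clinical Safety route.** This requires Sponsor approval and one of two grounds. The first is a request from a regulatory authority, ethics committee or IRB. The second is that "The Sponsor needs the information about the treatment assignment for the evaluation of risk analysis". Afterwards, "After unblinding, the CRO Clinical Safety Manager informs both the Sponsor and the Investigator about the study subject in question".

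The consequence for the subject is stated twice. Section 15.5.4.2 ends: "Subjects who are unblinded for emergency reasons will be discontinued from the treatment". Section 14.2.1 goes further: "The subject is withdrawn from the treatment and the study if the treatment arm is unblinded for emergency reasons", and, after a cross-reference to 15.5.4.2, "or for a reason other than the interim analysis before the end of the treatment".

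Section 14.2.2 asks that a subject who stops have the Visit 12 and Visit 13 evaluations, combined, as soon as possible. Both co-primary endpoints in Section 11.1.1 are defined from baseline to Day 171, and Section 10.1.4 allows no visit window for Visit 13. Section 15.7.3 handles missing effectiveness data by multiple imputation and leaves the detail to the SAP.

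**The concern.** An administrative or regulatory act, with no bearing on how the subject is treated, can end that subject's participation. The rule does not ask whether the site learned the arm. If the site stayed blind, there is no blinding reason to stop treatment. If the site did learn the arm, that may justify stopping treatment, but it does not require stopping measurement.

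At stake is an avoidable missing outcome on both co-primary endpoints. The gap follows a suspected device effect, so it may not be missing at random, which is the setting in which Section 15.7.3 justifies its imputation. The lesser matter is the blind: the text leaves open whether a site is told the arm when it has no clinical use for it.

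**Working it through.** **Step 1. Does the withdrawal rule reach the CRO route?** Yes. Section 15.5.4 counts management of a suspected USADE or SADE as emergency unblinding, so the first clause of the 14.2.1 sentence applies. If one doubted that, the second clause covers any other unblinding before the end of treatment except the interim analysis.

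**Step 2. Is the withdrawal automatic?** Yes. The reasons listed in 14.2.1 are applied by the Investigator after judging clinical relevance. The unblinding sentence stands after that list and carries no such condition.

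**Step 3. Does it depend on what the site knows?** No. The trigger is that the arm was unblinded. The notification sentence in 15.5.4.2 does not say whether the Investigator hears the assignment or only that the code was broken.

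**Step 4. What weight remains?** An exit weight taken soon after discontinuation (14.2.2). It coincides with Day 171 only if the code is broken near the end of treatment. No provision keeps the subject in follow-up to Day 171. The subject stays in the ITT population, defined as all randomized subjects (15.7.1.1). On the direct reading of 15.7.3 the Day 171 value is imputed. How the exit weight enters is left to the SAP.

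**Step 5. Whom does this concern?** Only subjects who could have continued. Under Section 14.1 subjects "may discontinue the study treatment for a period not exceeding 3 days for a valid medical reason", so a longer interruption already falls outside the permitted limit. Section 14.2.1 separately covers intolerance and the subject's best interest.

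**Step 6. How many?** The documents give no rate of suspected SADEs or of CRO-route code breaks. Their SAE figures for earlier studies are:

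- 95-subject single-administration study (5.2.1.1): no SAE.
- 12-week study (5.2.1.2): 3 subjects with SAEs among 43 on placebo, 3/43 = 7.0%; none reported among 42 + 41 = 83 on Gelesis100; overall 3/126 = 2.4%.

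Causality is not stated for those 3, so they are not counts of suspected SADEs and are not projected to this trial.

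**Step 7. Effect on power.** Inputs from Section 15.4: 460 randomized, 30% dropout, assumed difference 4.5%, margin 3.0%, SD 5.0%, one-sided 0.05.

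- Planned dropout: 460 × 0.30 = 138, leaving 322, or 161 per arm.
- Standardized effect: (4.5 − 3.0) / (5.0 × √(2/161)) = 2.692.
- Power: Φ(2.692 − 1.645) = Φ(1.047) = 85.2%, which reproduces the plan's 85%.

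Withdrawals on this route fall within the 138 already allowed for. As a stress test, assume instead that extra Day 171 weights are lost on top of the planned dropout:

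| Extra losses per arm (assumed) | Power |
|---|---|
| 1 | 85.0% |
| 2 | 84.8% |
| 3 | 84.7% |
| 5 | 84.2% |
| 10 | 83.2% |

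Even the last row, far above any plausible count for this route, costs 2 percentage points.

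**The case against.** The case against acting is substantial, and most of it stands.

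- **Rarity.** The situation needs a suspected SADE, a regulatory or sponsor request, Sponsor approval, timing before the end of treatment, and a subject well enough to go on. This stands, and it is why the severity is low.
- **The coupling is general.** Section 14.2.1 ties stopping the product to leaving the study for every listed reason, and 30% dropout is planned. This also stands. The missing Day 171 weight is not peculiar to the CRO route, and the fix reaches only one small source of it. Subjects stopped for intolerance, lipids or blood pressure would still leave.
- **The two sections can be reconciled.** Section 14.2.1 cross-refers to 15.5.4.2 and is the fuller rule. That is fair: the difference is an omission to tidy, not a contradiction on which the point depends.
- **Safety follow-up exists.** Section 13.1.3 already collects adverse events for 28 days after the last administration, and Section 13.3.1 requires follow-up of safety events. The fix preserves this and does not supply something absent.

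A reader might also infer two stronger things. The first is that the Investigator is told the arm, so the plan unblinds sites without need. The wording allows that reading but does not state it. The second is that assignments could reach the Steering Committee through its Sponsor and site members. Section 16.1 says that committee stays blinded throughout, and nothing in 15.5.4.2 authorizes passing assignments to it.

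What survives is narrow: an automatic study withdrawal triggered by a code break that may have no clinical or site-level blinding consequence.

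**Conclusion.** The point holds as a low-severity, inexpensive improvement. It rests on the text of 14.2.1 and 15.5.4.2 and on one assumption, that at least some subjects unblinded on this route could have continued. The likely gain is a handful of Day 171 weights at most, and possibly none; the documents do not allow an estimate.

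It would be wrong to infer that the trial is underpowered or that its conclusion is at risk. The planned 85% reproduces, and these withdrawals sit inside the dropout allowance. The possibility that such missing values are not random is a reason to avoid creating them. It does not show bias of any particular size or direction.

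**What to change.** **Section 15.5.4.2.** State that on the CRO Clinical Safety route the assignment goes only to the requesting body or to the sponsor safety staff who need it. State that the Investigator is told that the code was broken, but is told the arm only if treatment requires it.

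**Section 14.2.1.** Limit discontinuation triggered by unblinding to cases where the site learned the arm. Make it discontinuation of treatment only, with visits continued through Day 171 and the 28-day adverse event follow-up kept. The clinical reasons for stopping in 14.2.1 stay as they are, so a subject who should stop on medical grounds still does.

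**Alignment.** Reword the last sentence of 15.5.4.2 to match, so that it says what happens to study visits.

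**Cost.** The change is wording in the protocol and safety procedures. The sponsor study team loses immediate access to the arm for risk review; authorities still receive what they request, and emergency access for treatment is untouched. Section 19 requires a favorable ethics committee or IRB opinion before implementation, across about 38 sites (8.2), so the change should go into the next amendment and does not justify one of its own.
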